17.4.1. ECG MARKEDLY ABNORMAL CRITERIA

Markedly abnormal quantitative ECG measurements will be identified in accordance with the following predefined markedly abnormal criteria and summarized by time point and age category for QT interval and QTcF parameters.

- Absolute values for QT interval and QTcF will be classified as:
 - > 450 msec
 - > 480 msec
 - > 500 msec
- Change from Baseline for QT interval and QTcF will be classified as:
 - >30 msec increase from baseline
 - >60 msec increase from baseline

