7.4. EXAMINATION OF SUBGROUPS

No subgroup analyses will be performed for this study.

Document: C:\Users\q832483\Documents\Insy CSR\Pending\Ready for QC\New folder\Statistical Analysis Plan.docx
Author: [REDACTED] Version Number: V1.0 Final
Version Date: 04APR2017

Template No: CS_TP_BS016 – Revision 3
Effective Date: 01May2012

Reference: CS_WI_BS005

However analyses will be displayed by age category as follows:

- Infants = 1 to <2 years of age
- Children = 2 to <12 years of age
- Adolescents = 12 to ≤17 years of age

Age categories are based on the subject's age at the beginning of their previous study.

In addition, some relevant results observed during the follow-up period (between the Final visit and the Follow-up visit) or assessed at the Follow-up visit will be presented by CBD status (i.e. subjects who continue to receive CBD after their Final visit versus those who stop receiving CBD after their Final visit). Such analyses are further described in the following sections.

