17.4. ECG EVALUATIONS

Results from the central electrocardiogram (ECG) review will be included in the reporting of this study. If the first ECG is abnormal, up to an additional 2 repetitions of a specific assessment may be performed. ECG will be evaluated at Screening (for subjects who did not meet the rollover timing criteria, see [Section 6.2](#)), Day 1 and at Final Visit/Discontinuation Visit.

The following ECG parameters will be reported for this study:

- HR (Ventricular rate) (bpm)
- PR Interval (msec)
- QRS Interval (msec)
- QT Interval (msec)
- QTcF Interval (msec) [QT interval corrected by Fridericia]
- RR Interval (msec)
- Rhythm
 - Sinus rhythm
 - Atrial fibrillation
 - Other
- Overall assessment of ECG (Investigator's judgment):
 - Normal
 - Abnormal, Not Clinically Significant (ANCS)
 - Abnormal, Clinically Significant (ACS)

Handling of retests values is described [Section 6.3](#).

Document: C:\Users\q832483\Documents\Insy CSR\Pending\Ready for QC\New folder\Statistical Analysis Plan.docx
Author: [REDACTED] Version Number: V1.0 Final
Version Date: 04APR2017

Template No: CS_TP_BS016 – Revision 3
Effective Date: 01May2012

Reference: CS_WI_BS005

The following summaries will be provided for ECG data:

- Frequency counts and shift from baseline by age category (for qualitative measurements) in separate tables
- Summary of absolute results and change from baseline by age category (for quantitative measurements) in separate tables
- Absolute value and change from baseline according to markedly abnormal criteria and age category as described in [Section 17.4.1](#)
- Listing of all data with flag for subjects meeting markedly abnormal criteria for absolute values and for change from baseline

Each ECG result will be compared to the both baselines as defined [Section 6.2](#).

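### SAP 17.4.1 applies the same markedly abnormal cut-offs to uncorrected QT and to QTcF, so flags raised by QT alone depend on heart rate

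*SAP*

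**What the plan says.** SAP 17.4.1 (ECG Markedly Abnormal Criteria) defines two sets of limits, summarised by time point and age category. For the first, "Absolute values for QT interval and QTcF will be classified as" above 450, 480 or 500 msec. For the second, "Change from Baseline for QT interval and QTcF will be classified as" an increase above 30 or above 60 msec; the lower of these is written ">30 msec increase from baseline". Both sets cover both parameters, and neither varies with age or heart rate.

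SAP 17.4 (ECG Evaluations) identifies the corrected parameter as "QTcF Interval (msec) [QT interval corrected by Fridericia" and also reports heart rate and the RR interval. It asks for a listing that flags subjects who meet the absolute or the change criteria. On the reference value it says "Each ECG result will be compared to the both baselines as defined" in SAP 6.2, that is, the previous study's baseline and the intra-study baseline.

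The age categories in SAP 7.4 run from "Infants = 1 to <2 years of age" to "Adolescents = 12 to ≤17 years of age". SAP 6.5 rules out inferential procedures, so all ECG output is descriptive.

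**The concern.** Uncorrected QT shortens when the heart speeds up and lengthens when it slows. A correction formula exists to remove that dependence. A limit that suits the corrected interval therefore cannot carry the same meaning for the uncorrected one, except at the rate where the two coincide.

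Two faults follow, and they are worst at opposite ends of the heart-rate range. At slower rates a modest fall in heart rate is enough to produce a QT increase above 30 msec with QTcF unchanged. At faster rates the absolute 450 msec limit on QT is reached only when QTcF is far above 450.

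Change from baseline in ECG findings is a safety endpoint (protocol 6.1.6). A row headed markedly abnormal, or a flag against a child in a listing, should not be produced by heart rate alone. SAP 17.5.1 sharpens the contrast. It calls a low heart rate markedly abnormal only at 50 bpm or less combined with a fall of at least 15 bpm. A fall from 90 to 70 bpm is therefore unremarkable as a vital sign, yet its arithmetic effect on QT is labelled markedly abnormal.

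**Working it through.** The documents state no error rate or expected count for these criteria, so there is no figure of the plan's own to reproduce.

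**Inputs from the SAP.** Absolute limits 450/480/500 msec and increases 30/60 msec (17.4.1); Fridericia correction (17.4); heart-rate criterion (17.5.1).

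**Assumptions, not in the documents.** Starting heart rate 70 to 120 bpm; QTcF 400 msec (380 to 440 as a check); SD of heart-rate change between two ECGs 10 to 20 bpm, mean change zero.

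**Step 1: the relation.** With RR = 60/HR in seconds, QTcF = QT / RR^(1/3), so QT = QTcF x (60/HR)^(1/3). The factor equals 1 only at 60 bpm.

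**Step 2: QTcF at which QT reaches 450.** QTcF = 450 / (60/HR)^(1/3). At 100 bpm: 450 / 0.843 = 534 msec.

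**Step 3: heart-rate fall that raises QT by 30 msec with QTcF at 400.** Solve 400 x (60/h)^(1/3) = 400 x (60/HR)^(1/3) + 30 for the new rate h:

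h = 60 / [(60/HR)^(1/3) + 30/400]^3.

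From 70 bpm: 60 / (0.950 + 0.075)^3 = 55.7, a fall of 14.3 bpm.

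**Step 4: chance of a false flag above 30 msec per comparison.** P = 1 - Φ(fall / SD), with QTcF constant.

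| Starting HR (bpm) | QTcF at QT 450 (msec) | New HR at +30 msec | Fall (bpm) | P, SD 10 | P, SD 15 | P, SD 20 |
|---|---|---|---|---|---|---|
| 70 | 474 | 55.7 | 14.3 | 7.7% | 17% | 24% |
| 80 | 495 | 63.1 | 16.9 | 4.5% | 13% | 20% |
| 90 | 515 | 70.3 | 19.7 | 2.4% | 9% | 16% |
| 100 | 534 | 77.4 | 22.6 | 1.2% | 6.6% | 13% |
| 120 | 567 | 91.5 | 28.5 | 0.2% | 2.9% | 7.7% |

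Every new rate in the table is above 50 bpm, so none of these falls would meet the low heart-rate criterion of SAP 17.5.1.

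**Checks.**
- A fall from 120 to 90 bpm gives 400 x (0.8736 - 0.7937) = 32.0 msec. A fall from 90 to 70 gives 400 x (0.9499 - 0.8736) = 30.5 msec.
- Varying QTcF from 380 to 440 moves the required fall only to 13-15 bpm from 70, 21-24 from 100 and 26-30 from 120.
- The 60 msec rule is harder to trip: the fall must be about 25 bpm from 70, 39 from 100 and 49 from 120.
- Applied to QTcF, the same pure rate change gives an increase of 0 msec under the Fridericia relation.

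**The case against.** The strongest reply is that nothing is lost. QTcF is classified by the same rules in parallel, heart rate and RR are reported, the ECGs are centrally reviewed, an investigator's overall assessment is recorded, and nothing is tested. The withdrawal criteria in protocol 3.4.3 name no QT limit. On this view the QT rows are merely redundant, and a footnote would do. That argument stands as a limit on the harm, and it rules out several stronger readings.

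- *A real QTcF rise goes unflagged.* A reader might take a child whose QTcF goes from 400 to 460 msec while heart rate rises from 100 to 120 bpm. QT then rises by only 460 x 0.7937 - 400 x 0.8434 = 27.7 msec, below the QT change limit. But the same child is flagged on QTcF twice, for exceeding 450 and for an increase above 30. Only the QT row misses it.
- *A rate-driven QT rise cannot be told from a drug effect, or the QT rows falsely reassure.* The planned output shows QT, QTcF, HR and RR together, so a QT rise with flat QTcF and a slower rate can be recognised.
- *The 450 msec limit on QT is out of reach throughout ages 1 to 17.* At 60 to 70 bpm a QTcF of 450 to 474 is enough. The documents do not say which rates the age groups will have.
- *A definite number of the 80 children will be falsely flagged.* Heart-rate variability is not given, ECGs follow at least 5 minutes supine (protocol 6.1.5.3), and 80 is the maximum enrolment, not the number with paired ECGs.
- *Sedation will slow the heart and create the signal.* Somnolence, sedation and lethargy are events of special interest, but the documents do not link them to heart rate.
- *There is only one post-baseline ECG.* That holds for the intra-study baseline. Against the previous study's baseline the Day 1 ECG counts as well.

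Nor does the SAP describe these as limits meant for corrected intervals; the argument rests only on its own correction formula. What the objection does not answer is why a child with unchanged QTcF should carry a markedly abnormal label at all.

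**Conclusion.** The point holds in a limited form. The shared cut-offs agree only at 60 bpm, so the markedly abnormal counts and flags for uncorrected QT partly follow heart rate. With QTcF at 400 msec, a fall of about 14, 20 or 29 bpm from 70, 90 or 120 bpm brings QT to the 30 msec change limit. The insensitivity of the 450 msec limit is a separate fault, confined to faster rates.

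The frequency cannot be fixed from the documents. The range of roughly 0 to 24% per comparison assumes a normally distributed heart-rate change with mean zero, constant QTcF and an exact Fridericia relation. The change rows are produced for each of the two baselines, so a rate-driven flag can arise in either. No QTcF count and no inference is affected. The damage is misleading QT rows and QT-only listing flags, which makes this a cheap improvement rather than a threat to the study's conclusions.

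**What to change.** In SAP 17.4.1, restrict the absolute (450/480/500 msec) and change (30/60 msec) criteria to QTcF, in the summary table and in the listing flags described in SAP 17.4. Keep uncorrected QT in the descriptive summaries and in the listing, beside HR and RR.

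The cost is an SAP edit and fewer table rows; no new data are needed, since QTcF is already reported. Protocol 8.3.4.4 asks for flags on absolute and change values but sets no QT-specific limits. Protocol 8.2.1 lets changes in statistical methods before database lock be documented in the SAP without a protocol amendment. The one loss is an outlier row for uncorrected QT. A footnote telling readers to interpret QT with heart rate would be a weaker alternative, because the label and flag would remain.

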17.5. VITAL SIGNS

The following Vital Signs measurements will be reported at each visit:

- Systolic Blood Pressure (mmHg)
- Diastolic Blood Pressure (mmHg)
- Pulse Rate (bpm)
- Respiratory Rate (breaths/min)
- Temperature (°C)

If clinically significant findings, as determined by the Investigator, occur in any of the vital signs measurements, that measurement will be repeated at medically appropriate intervals until the value returns to an acceptable range, a specific diagnosis is established, or the condition is otherwise explained.

Document: C:\Users\q832483\Documents\Insy CSR\Pending\Ready for QC\New folder\Statistical Analysis Plan.docx
Author: [REDACTED] Version Number: V1.0 Final
Version Date: 04APR2017

Template No: CS_TP_BS016 – Revision 3
Effective Date: 01May2012

Reference: CS_WI_BS005

The following summaries will be provided for vital signs data:

- Actual and change from baseline by time point and age category
- Incidence of markedly abnormal values
- All vital signs will be listed

Each vital sign result will be compared to the both baselines as defined [Section 6.2](#).

Each vital sign result measured at the Follow-up visit will also be summarized (as described above) by CBD status.

In addition, the subject weight will be summarized in terms of both:

- Change from baseline across each visit
- Change from baseline to Follow-up visit by CBD status

The corresponding listing will also be provided including the flag for CBD status.

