6.6. COMMON CALCULATIONS

For quantitative measurements, change from baseline will be calculated as:

- Test Value at Visit X – Baseline Value

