10. DEMOGRAPHIC AND OTHER BASELINE CHARACTERISTICS

Demographic data and other baseline characteristics will be presented for the SAF by age category and overall.

No statistical testing will be carried out for demographic or other baseline characteristics.

The following demographic and other baseline characteristics will be reported for this study:

Document: C:\Users\q832483\Documents\Insy CSR\Pending\Ready for QC\New folder\Statistical Analysis Plan.docx
Author: [REDACTED] Version Number: V1.0 Final
Version Date: 04APR2017

Template No: CS_TP_BS016 – Revision 3
Effective Date: 01May2012

Reference: CS_WI_BS005

- Age (years) - calculated relative to date of consent
- Gender
- Race
- Ethnicity
- Weight (kg)
- Height (cm)

For height and weight, the baseline value of the previous study will be reported for subjects who were enrolled no later than 14 days after they completed their previous study. Otherwise, height and weight will be from the screening physical examinations for this study.

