APPENDIX 2. ADVERSE EVENTS OF SPECIAL INTEREST PREFERRED TERMS

- Anemia;
- Diarrhea;
- Fatigue;
- Blood FSH decreased;
- Blood FSH increased;
- Weight decreased;
- Weight increased;
- Decreased appetite;
- Hypersomnia;
- Lethargy;
- Sedation;
- Seizure;
- Somnolence;
- Status epilepticus;
- Aggression;
- Agitation;
- Irritability;
- Acute respiratory failure;
- Dyspnea;
- Respiratory arrest.

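### Weight is summarised only as simple change from baseline in growing children, so normal growth can mask weight faltering in the quantitative tables

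*SAP*

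**What the plan says.** SAP 17.5 adds weight at the end of the vital signs section. It says that "the subject weight will be summarized in terms of both" of two measures, "Change from baseline across each visit" and "Change from baseline to Follow-up visit by CBD status", and it adds a subject listing that flags CBD status. SAP 6.6 defines change for any quantitative measurement as "Test Value at Visit X – Baseline Value". SAP 10 reports weight in kilograms.

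The markedly abnormal criteria in SAP 17.5.1 cover blood pressure, heart rate, temperature and respiratory rate, but not weight. Respiratory rate is given age-dependent ranges there. Height is measured at every physical examination (SAP 17.6), but the only numerical summary planned for it is as a baseline characteristic (SAP 10).

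SAP 7.4 displays analyses in three age categories. The lower two are "Infants = 1 to <2 years of age" and "Children = 2 to <12 years of age", and the third runs from 12 to 17 years. SAP Appendix 2 lists "Weight decreased" as an adverse event of special interest, along with weight increase and decreased appetite.

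SAP 6.2 defines two baselines: Baseline 1 from the previous study, and Baseline 2, the last non-missing value before first dose in this study. SAP 17.5 applies both to each vital sign result. Weight is not in that list of vital signs, and the weight bullets name no baseline.

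**The concern.** In an adult study, a mean weight change near zero is the natural null. In children it is not, because a child whose growth is unaffected gains weight over 48 weeks. The planned summary measures change against zero, when the safety question is change against expected growth.

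Three features of the design make this matter:

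- There is no control arm (Protocol 4.8 describes an open-label study), so the trial cannot estimate expected gain internally.
- Protocol Table 1 schedules physical examinations, and with them weight, at Day 1, Weeks 24 and 36, the Final Visit and Follow-up. For a subject entering at Day 1, the first scheduled post-baseline weight already contains about 24 weeks of growth.
- The middle age stratum is ten years wide, so the same kilogram change has a very different meaning for different children within it.

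Long-term safety is the primary objective (SAP 2.1), and the plan itself names weight and appetite as special interests. At stake is a positive mean change that gives more reassurance than it should.

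**Working it through.** The documents state no expected weight gain, effect size or weight threshold, so there is no planned figure to reproduce. The check is a reading of the SAP sections above followed by an illustration. All growth inputs below are assumptions.

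**1. Group mean.** Let g be the expected 48-week gain, f the share of children affected, and s the share of expected gain that an affected child loses. Then mean raw change = g × (1 − f × s).

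| Scenario | g = 1.5 kg | g = 5 kg |
|---|---|---|
| Every child loses half (f = 1, s = 0.5) | +0.75 kg | +2.5 kg |
| Half the children gain nothing (f = 0.5, s = 1) | +0.75 kg | +2.5 kg |
| Every child loses 75% (f = 1, s = 0.75) | 1.5 × 0.25 = +0.38 kg | 5 × 0.25 = +1.25 kg |

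Under this model the mean reaches 0 only if every child stops gaining (f × s = 1).

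**2. The child who gains nothing.** The raw change is 0 kg. The shortfall is expected gain divided by starting weight. The approximate z-score shift is ln(actual weight / expected weight) / CV, with an assumed CV of weight-for-age of 0.10 to 0.15.

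| Assumed start, expected gain | Shortfall | Log ratio | z shift (CV 0.10 to 0.15) |
|---|---|---|---|
| 10 kg, 2 kg | 2/10 = 20% | ln(10/12) = −0.182 | −1.82 to −1.22 |
| 20 kg, 2.5 kg | 2.5/20 = 12.5% | ln(20/22.5) = −0.118 | −1.18 to −0.79 |
| 45 kg, 4 kg | 4/45 = 8.9% | ln(45/49) = −0.085 | −0.85 to −0.57 |

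So 0 kg in the planned table corresponds to a fall of roughly 0.6 to 1.8 z.

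**3. Mixing ages.** A gain of 1 kg is 10% of a 10 kg child and 2% of a 50 kg child. If expected gain is spread evenly over 1.5 to 5 kg, normal growth alone gives raw change an SD of (5 − 1.5)/√12 = 1.0 kg.

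**The case against.** The strongest reply is that SAP 17.5 is not the only route by which a weight problem can surface, and this is correct. Special-interest terms are tabulated by system organ class, preferred term, relationship and severity (SAP 17.1.6). A finding that the investigator judges clinically significant becomes an adverse event (Protocol 6.1.5). Physical examination results are summarised by clinical significance, with shifts from baseline (SAP 17.6). Individual weights are listed, and listings go to the sponsor periodically for safety review (SAP 4.2).

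A reader might therefore infer from this point that the plan cannot detect a weight effect, or that a child who fails to gain is never counted. The documents do not support that. A true loss in kilograms would show in the minimum and the listing, and an investigator can report poor gain. What stands is narrower: these routes depend on judgement without a numeric weight threshold, and the quantitative tables themselves can mask faltering.

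A reader might also put the shortfall as high as 25% by setting 4 kg a year (4 × 48/52 = 3.7 kg) against a 15 kg child. That pairs the top of an assumed range with a small child, and nothing in the documents justifies the pairing. With gain matched to size, the range is about 9 to 20%.

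Two further replies carry some weight. The study is descriptive with no inference (SAP 6.5), and the data permit z-scores to be derived later, so nothing is lost irretrievably. Also, table content follows templates supplied with the SAP (SAP 8), which are not in the text reviewed. The absence of a growth measure is therefore established for the SAP text, not for the templates.

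**Conclusion.** The point holds for the quantitative weight summaries. They give a simple difference in kilograms, with no growth standard and no weight criterion, for subjects aged 1 to 17 followed for up to about 48 weeks. Subjects from INS011-15-054 are followed for less time within this study, because the two studies together are capped at about 48 weeks. The kilogram reading is inferred from SAP 6.6 and SAP 10, since 17.5 does not state it.

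On the assumed growth figures, the mean remains at about +0.4 to +1.25 kg even when every child loses three quarters of an expected 1.5 to 5 kg. A zero-gain child is about 9 to 20% of starting weight behind. The direction of the masking follows from growth itself, but its size rests wholly on those assumptions.

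A reader might infer from SAP 10 that weight change is measured from the wrong starting point, because for prompt rollovers "the baseline value of the previous study will be reported for subjects who were enrolled no later than 14 days". That rule governs the demographic table, not change from baseline. The gap is only that SAP 17.5 does not say which baseline weight uses.

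This should be changed because it concerns a named special interest within the primary objective. It does not defeat that objective.

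**What to change.** In SAP 17.5:

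- Add change in age- and sex-standardised weight-for-age and height-for-age z-scores from a named growth reference, by visit, by age category, and by CBD status at Follow-up. Compute them from exact age on the day of measurement; the whole-year age in SAP 10.1 is too coarse.
- Tabulate n (%) of subjects whose z-score falls by an amount fixed in the SAP before database lock. In the illustration a zero-gain 45 kg subject falls only about 0.6 to 0.9 z, so a cut-off above that would miss such a subject.
- State that weight change uses both SAP 6.2 baselines, with Baseline 2 as the extension baseline. Naming a fixed Visit 2 weight would be worse: Protocol 5.2.1 allows assessments from the preceding 14 days to stand in for Visit 2, and the entry visit for INS011-15-054 subjects is discretionary (Protocol 3.1).
- Optionally, count subjects with weight loss of ≥5% and ≥10%. This captures actual loss only, because a child who gains nothing shows 0%.

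The cost is SAP text and derived variables. Date of birth, sex, height and weight are already collected, and no visit, procedure or sample size changes.

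There are two limits. A general growth reference may fit severely disabled children less well. A fall in z-score also cannot be attributed to the drug alone, because background antiepileptic drugs and ketogenic diet may change during the study (Protocol 4.3), and Protocol 1.2 itself links valproic acid and topiramate to weight change.

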17.5.1. VITAL SIGNS MARKEDLY ABNORMAL CRITERIA

Markedly abnormal quantitative Vital Signs measurements will be identified in accordance with the following predefined markedly abnormal criteria:

Variable	Unit	Low	High
SBP	mmHg	≤ 90 mmHg AND change from baseline ≤ -20 mmHg	≥ 180 mmHg AND change from baseline ≥ 20 mmHg
DBP	mmHg	≤ 50 mmHg AND change from ≤ -15 mmHg	≥ 105 mmHg AND change from baseline ≥ 15 mmHg
Heart rate	Bpm	≤ 50 bpm AND change from baseline ≤ -15 bpm	≥ 120 bpm AND change from baseline ≥ 15 bpm
Body temperature	°C	NA	≥ 38.3 °C AND change from baseline ≥ 1.1 °C

Respiratory rate will be classified as Low and High according to the following age-dependent ranges (Low for values under the range and High for values above the range):

Age Category	Normal Respiratory Rate Range (Breaths Per Minute)
< 3 years	20-30 bpm
3 -< 6 years	20-25 bpm

Document: C:\Users\q832483\Documents\Insy CSR\Pending\Ready for QC\New folder\Statistical Analysis Plan.docx
Author: [REDACTED] Version Number: V1.0 Final
Version Date: 04APR2017

Template No: CS_TP_BS016 – Revision 3
Effective Date: 01May2012

Reference: CS_WI_BS005

6 < 12 years	14-22 bpm
≥ 12 years	12-18 bpm

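### The high blood-pressure flags and the low heart-rate flag need one all-ages limit AND a change, so they can hardly fire in young children

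*SAP*

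**What the plan says.** SAP 17.5.1 defines six blood-pressure and heart-rate flags. Each joins an absolute limit to a change from baseline, and none has an age term:

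- Systolic high: "≥ 180 mmHg AND change from baseline ≥ 20 mmHg"
- Systolic low: "≤ 90 mmHg AND change from baseline ≤ -20 mmHg"
- Diastolic high: "≥ 105 mmHg AND change from baseline ≥ 15 mmHg"
- Diastolic low: "≤ 50 mmHg AND change from ≤ -15 mmHg" (the cell omits the word baseline; I read it like the others)
- Heart rate high: "≥ 120 bpm AND change from baseline ≥ 15 bpm"
- Heart rate low: "≤ 50 bpm AND change from baseline ≤ -15 bpm"

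SAP 7.4 displays results in three age categories. The youngest is "Infants = 1 to <2 years of age" and the oldest runs to 17 years.

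In the same section, respiratory rate is treated differently: "Respiratory rate will be classified as Low and High according to the following age-dependent ranges". There are four bands (under 3, 3 to under 6, 6 to under 12, and 12 years or older) and no change criterion. SAP 17.4.1 classifies QT and QTcF by absolute value and, separately, by change from baseline.

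SAP 17.5 plans three outputs: actual values and changes by time point and age category, the incidence of markedly abnormal values, and a listing of all vital signs. Protocol 8.3.4.3 commits to tabulating both notable values and notable changes.

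**The concern.** Under an AND rule the harder condition decides. If a child's usual value lies far from the absolute limit, meeting the limit already implies a change much larger than the stated one, and the change criterion does no work. The limits do not vary with age although the subjects run from 1 to 17 years, and the SAP itself accepts age dependence for respiratory rate.

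Long-term safety is the primary objective (SAP 2.1), and change in vital signs is a named safety endpoint (Protocol 6.1.6). The incidence table is the planned output that counts subjects with a notable vital sign. If some of its flags can hardly fire in the youngest children, a zero in those cells could be taken as reassurance that the rule was not able to give.

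**Working it through.** The section states thresholds and no computed figure, so there is nothing to reproduce. The check is how large a change each rule requires.

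**Inputs.** Limits and change criteria come from SAP 17.5.1. The documents give no vital signs by age, so resting values are assumptions, shown over a range.

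**Formulas.**
- Smallest rise flagged high = max(change criterion, limit − baseline). The change criterion decides only if baseline ≥ limit − change.
- Smallest fall flagged low = max(change criterion, baseline − limit). The change criterion decides only if baseline ≤ limit + change.

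**Step 1: where the stated change decides (no assumption needed).**

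| Flag | Limit | Change | Change decides only at baseline |
|---|---|---|---|
| Systolic high | 180 | 20 | ≥ 180 − 20 = 160 mmHg |
| Diastolic high | 105 | 15 | ≥ 105 − 15 = 90 mmHg |
| Heart rate low | 50 | 15 | ≤ 50 + 15 = 65 bpm |
| Systolic low | 90 | 20 | ≤ 90 + 20 = 110 mmHg |
| Diastolic low | 50 | 15 | ≤ 50 + 15 = 65 mmHg |
| Heart rate high | 120 | 15 | ≥ 120 − 15 = 105 bpm |

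**Step 2: change needed for the first three flags at assumed baselines.**
- Systolic high, baseline 85–110 mmHg: 180 − 110 = 70 to 180 − 85 = 95 mmHg. Over a wider range: 100 at baseline 80, 60 at 120, 50 at 130.
- Diastolic high, baseline 45–65 mmHg: 105 − 65 = 40 to 105 − 45 = 60 mmHg. At baseline 85 it is 20.
- Heart rate low, baseline 100–120 bpm: 100 − 50 = 50 to 120 − 50 = 70 bpm. It is 90 at baseline 140 and 20 at baseline 70.

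**Step 3: the other three flags at the same baselines.**
- Systolic low, baseline 85–110 mmHg: a fall of 20 is enough throughout.
- Diastolic low, baseline 45–65 mmHg: a fall of 15 is enough throughout.
- Heart rate high: a rise of 15 is enough from baseline 105 bpm up. At 100 it is 120 − 100 = 20.

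**Step 4: the two directions compared.**
- Assumed systolic 95 mmHg: a fall of 20 flags; a rise must reach 180 − 95 = 85.
- Assumed heart rate 110 bpm: a rise of 15 flags; a fall must reach 110 − 50 = 60.

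Equal and opposite changes are thus counted in one direction only. With two flags each for systolic pressure, diastolic pressure, heart rate and respiratory rate, and one for temperature, the section has 9 flag types. Three of them are affected in this way.

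**The case against.** A reader might infer that blood-pressure and heart-rate changes in young children cannot be flagged at all, or that the abnormality table for the youngest groups would be nearly empty. The documents do not support either. Systolic low, diastolic low and heart rate high fire at about the stated change when pressure is low or heart rate is high. If anything, their limits filter too little there. Temperature and respiratory rate flag as well. Even the three affected flags can fire, but only at very large changes.

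The endpoint is also analysed elsewhere. SAP 17.5 summarises actual values and changes by age category against both baselines and lists every value. The protocol's descriptive statistics include minimum and maximum (Protocol 8.2.2), so an extreme change at a scheduled visit would show. Under Protocol 6.1.5, a finding that the investigator judges clinically significant is an adverse event. The study makes no inference (SAP 6.5).

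All of this stands, and it limits the point to one descriptive table. It does not remove it. Means and extremes do not count subjects with a notable change. SAP 6.3 keeps unscheduled measurements out of by-visit summaries. The adverse event route depends on judgement and lets findings that fit a current diagnosis be documented otherwise.

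A further fair objection is that the sizes in steps 2 to 4 rest on assumed baselines. The cut-points in step 1 do not.

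**Conclusion.** The point holds for three flags: systolic high, diastolic high and heart rate low. Their stated change criteria (20 mmHg, 15 mmHg, 15 bpm) decide nothing unless baseline is at least 160 mmHg systolic, at least 90 mmHg diastolic, or at most 65 bpm. On the assumed resting values, a systolic-high flag needs a rise of 70–95 mmHg and a heart-rate-low flag a fall of 50–70 bpm. A zero count for these flags in young children is therefore weak evidence of safety, and an imbalance between directions in the table may come from the rule rather than the drug.

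The lack of an age term makes this worse in the youngest, but the AND is the main cause: at an assumed systolic baseline of 130 mmHg the rise needed is still 50.

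The loss does not reach beyond the incidence table. The conclusion that the three rules rarely operate assumes that young children's baselines lie well away from the step 1 cut-points. The trial's own baseline data can confirm that.

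**What to change.** In SAP 17.5.1, tabulate the absolute criteria and the change criteria separately. The change counts use the SAP's own numbers in both directions: ±20 mmHg systolic, ±15 mmHg diastolic, ±15 bpm heart rate. This follows the layout of SAP 17.4.1 for QT and QTcF and gives the count of notable changes that Protocol 8.3.4.3 promises. The combined flag can stay as an extra row. State in SAP 17.5 that the incidence table is shown by age category; its entry there does not say so, although SAP 7.4 sets that display in general. Supply the missing word in the diastolic-low cell.

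Optionally, the sponsor may also prespecify blood-pressure and heart-rate limits in the four age bands already used for respiratory rate. This is secondary: the documents contain no paediatric reference for such limits, so none are suggested here.

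The cost is SAP text and programming, with no new data. The downside is more flags to review, mainly in small children.
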